6.6.2. Interim Immunogenicity Review

No interim immunogenicity analysis is planned. Should emergent public health needs dictate interim immunogenicity review, immune responses will be summarized in terms of strain-specific 2013 and 2017 A/H7N9 HAI and Neut antibody titers and the relationship to study vaccine dosage, adjuvant use and study vaccination schedule. It is anticipated that all analyses will be carried out in parallel for both assays, but reports may be prepared separately for HAIs and Neuts if results are available on different timelines. Interim analyses will focus on rates of titers $\geq 1:40$, seroconversion (see definition in Section 3.3) and GMTs, along with corresponding 95% CIs. No formal hypothesis testing will be included in the interim analysis, and interim results will not have impact on conduct of this trial. All interim analyses will use the mITT population.

Any immunogenicity reports would be provided by the SDCC to the DMID Scientific Lead, DMID Clinical Project Manager and DSMB. Reports will include data summarized by unblinded study group, but the presentation will be in a format that prevents inadvertent unblinding of any individual subject.

There is no plan to halt this trial prior to full enrollment and completion of all follow-up visits based on any interim immunogenicity results.

6.7. Multicenter Studies

Randomization was stratified by site, but data will be pooled across all clinical sites for all analyses. Center effects are not anticipated because the sites use standardized procedures for vaccination and assessment of solicited and unsolicited AEs, and the study relies on a central laboratory for immunogenicity assessments.

6.8. Multiple Comparisons/Multiplicity

This study was designed to obtain preliminary estimates of safety and immune response to the 2013 and 2017 A/H7N9 vaccinations in healthy adults. The study was not designed to test any specific null hypothesis, and as such no adjustment for multiple comparisons will be performed.

7. STUDY SUBJECTS

7.1. Disposition of Subjects

[Table 14](#) will present a summary of the reasons that subjects were screened but not enrolled.

The number and percentage of enrolled subjects excluded from each analysis population by study group are presented in [Table 15](#). A listing of subjects excluded from each analysis population will be presented in [Listing 5](#).

The disposition of subjects in the study will be tabulated by study group ([Table 16](#)). The table will show the total number of subjects screened, randomized, receiving the first vaccination, receiving the second vaccination, completing the blood draw for the primary immunogenicity endpoints, and completing the last visit.

A flowchart showing the disposition of study subjects, adapted from the CONSORT Statement [4] will be included and will present the number of subjects screened, randomized, lost to follow up, and analyzed, by study group ([Figure 1](#)).

A listing of subjects who were discontinued from treatment or terminated from study follow-up and the reason will be included in [Listing 2](#).

7.2. Protocol Deviations

A summary of subject-specific protocol deviations will be presented by the deviation category and deviation type, and study group for all enrolled subjects ([Table 9](#)). Major deviations that will be reviewed for possible exclusion of immunogenicity results from the PP population include deviations related to eligibility/enrollment, treatment administration schedule, follow-up visit schedule, and receipt of exclusionary vaccines or medications. All subject-specific protocol deviations and non-subject-specific protocol deviations will be included in [Listing 3](#) and [Listing 4](#).

8. IMMUNOGENICITY EVALUATION

Immunogenicity data summaries and analysis for primary and secondary endpoints will be presented for the mITT population, which is the primary population for analysis. The Per Protocol population displays will be generated only if >10% of subjects are found to have data excluded from a primary or secondary timepoint. Immune responses in terms of strain-specific 2013 and 2017 A/H7N9 HAI and Neut antibody titers will be summarized by study group at each time point. Descriptive summary statistics will be provided for all assays and time points including number of subjects with non-missing results, percentage of subjects with titers $\geq 1:40$, percentage of subjects achieving seroconversion, and GMTs along with corresponding 95% CI. Exact confidence intervals will be presented for proportional endpoints. Summaries of primary and secondary immunogenicity endpoints are presented for the 2013 A/H7N9 strain in [Table 24](#), [Table 25](#), [Table 26](#), and [Table 27](#) and for the 2017 A/H7N9 strain in [Table 28](#), [Table 29](#), [Table 30](#), and [Table 31](#).

Reverse cumulative distribution (RCD) curves will be presented for post-vaccination HAI and Neut antibody titers. Plots for each assay will be generated with 3 columns (Day 22 post vaccination 1, Day 22 post vaccination 2, and Day 181 post vaccination 2) and 2 rows (2013 A/H7N9, 2017 A/H7N9), and separate curves within each panel for each study group, as shown in [Figure 2](#), [Figure 3](#), [Figure 4](#), and [Figure 5](#).

Figures depicting the HAI and Neut GMT over time will also be presented as shown in [Figure 6](#), [Figure 7](#), [Figure 8](#), and [Figure 9](#) for both 2013 and 2017 A/H7N9 strains.

The spearman correlation between HAI and Neut antibody titers will be calculated at each time point over all groups. The correlation will be depicted in scatter plots as [Figure 10](#) and [Figure 11](#) for both the 2013 and 2017A/H7N9 strain.

Individual HAI and Neut assay results will be provided in [Listing 9](#).

8.1. Primary Immunogenicity Analysis

The primary immunogenicity endpoints HAI and Neut seroconversion, percentage of subjects with titer $\geq 1:40$, and GMTs against the 2013 and 2017A/H7N9 vaccine strains 21 days after the second vaccination will be summarized as described above. The primary analysis population will be mITT, with results from the PP population providing a comparison of the sensitivity of immunogenicity results to subject adherence to protocol-defined conditions. Regression modelling of seroconversion and log titers is planned as described in [Section 8.3.2](#).

8.2. Secondary Immunogenicity Analyses

The secondary immunogenicity endpoints HAI and Neut seroconversion, percentage of subjects with titer ≥ 40 , and GMTs against the 2013 and 2017 A/H7N9 vaccine viruses prior to each study vaccination, 21 days after the first vaccination and 180 days after the second vaccination will be summarized as described above. No formal hypothesis testing is planned.

8.3. Exploratory Immunogenicity Analyses

Exploratory immunogenicity data summaries and analysis for exploratory endpoints will be presented for the PP population if >10% of subjects are found to have data excluded from a primary or secondary timepoint. Otherwise, exploratory displays will be presented for the modified intent to treat population.

8.3.1. HAI and Neut Covariate Analysis

As an exploratory analysis, seroconversion and GMT of serum antibody for both HAI and Neut against the homologous 2013 A/H7N9 strain at 21 and 180 days after the second study vaccination will be summarized by study group stratified by age (categorized as those subjects ages 19-34, 35-50 years) (Table 32, Table 33, Table 34, and Table 35), by sex (Table 40, Table 41, Table 42, and Table 43), by BMI (Table 48, Table 49, Table 50, and Table 51), and by prior receipt of the 2016-2017 and/or 2017-2018 and /or 2018-2019 seasonal influenza vaccines (Table 56, Table 57, Table 58, and Table 59). These analyses will be repeated for HAI and Neut titer results against the 2017 A/H7N9 strain at 21 and 180 days post receipt of the second study vaccination by age category (Table 36, Table 37, Table 38, and Table 39) by sex (Table 44, Table 45, Table 46, and Table 47), by BMI (Table 52, Table 53, Table 54, and Table 55) by prior receipt of seasonal influenza vaccine (Table 60, Table 61, Table 62, and Table 63).

The stratified summaries will be presented for the PP population. It is anticipated that subjects will have little to no pre-existing antibody at baseline, so seroconversion and titer ≥ 40 endpoints will be similar.

8.3.2. HAI and Neut Regression Modeling

Regression modeling will be utilized to test for the effect of treatment variables i.e. prime boost combination (*PrimeBoost*), Boost dose (*BoostDose*), and interval between vaccinations (*Interval*), on immune response. Logistic regression will be fit for the seroconversion outcome. If the available titer data meet the required assumptions of normality after log transformation, multiple linear regression will be fit to log-transformed titers. Separate models will be fit for each assay (HAI, Neut), each strain (2013 A/H7N9, 2017 A/H7N9) and each time point (Day 22 post vaccination 1, Day 22 post vaccination 2, Day 181 post vaccination 2). All models will be fit with a similar structure for *PrimeBoost*, *BoostDose*, *Interval*, and covariates, for the PP population. The treatment variables will be defined as *PrimeBoost* (homologous, heterologous), *BoostDose* (3.75 mcg+AS03, 15 mcg), and *Interval* (21 days, 120 days). All models will be fit with and without adjustment for the following covariates (*Z*): age in years, sex (female, male), BMI (<30, ≥ 30), and prior receipt of seasonal influenza vaccine in the current season (did not receive 2018-2019 seasonal influenza vaccine, received 2018-2019 seasonal influenza vaccine) (did not receive 2016-2017 or 2017-2018 seasonal influenza vaccines, received 2016-2017 and/or 2017-2018 seasonal influenza vaccine). The models as shown below assume a linear relationship between age in years and both probability of seroconversion and GMT. The validity of this assumption will be assessed prior to analysis and, if the relationship between age and response is found to be non-linear, adjustments will be made to model parameters to satisfy regression assumptions. Modeling assumptions will be checked using standard diagnostic methods (e.g., using the INFLUENCE option in PROC LOGISTIC or PROC GLM). Parameter estimates and odds ratio estimates for the logistic models will be presented for the 2013 and 2017 A/H7N9 strains without covariate adjustment in Table 64, Table 65, Table 66, Table 67, and with covariate adjustment in Table 68, Table 69, Table 70, Table 71. Parameter estimates for the multiple linear regression models will be presented for the 2013 and 2017 A/H7N9s strain without covariate adjustment in Table 72, Table 73, Table 74, Table 75, and with covariate adjustment in Table 76, Table 77, Table 78, Table 79.

Model 1A: Logistic Regression (without covariate adjustment):

$$\begin{aligned} \text{logit}[P(\text{seroconversion})] \\ = \beta_0 + \beta_1 \times \text{PrimeBoost} + \beta_2 \times \text{BoostDose} + \beta_3 \times \text{Interval} \\ + \beta_4 \times (\text{PrimeBoost} * \text{BoostDose}) + \beta_5 \times (\text{PrimeBoost} * \text{Interval}) + \varepsilon \end{aligned}$$

Model 1B: Logistic Regression (with covariate adjustment):

$$\begin{aligned} \text{logit}[P(\text{seroconversion})] &= \beta_0 + \beta_1 \times \text{PrimeBoost} + \beta_2 \times \text{BoostDose} + \beta_3 \times \text{Interval} \\ &+ \beta_4 \times (\text{PrimeBoost} * \text{BoostDose}) + \beta_5 \times (\text{PrimeBoost} * \text{Interval}) + \beta_6 \times Z + \varepsilon \end{aligned}$$

Model 2A: Multiple Linear Regression (without covariate adjustment):

$$\begin{aligned} \log(\text{titer}) &= \beta_0 + \beta_1 \times \text{PrimeBoost} + \beta_2 \times \text{BoostDose} + \beta_3 \times \text{Interval} \\ &+ \beta_4 \times (\text{PrimeBoost} * \text{BoostDose}) + \beta_5 \times (\text{PrimeBoost} * \text{Interval}) + \varepsilon \end{aligned}$$

Model 2B: Multiple Linear Regression (with covariate adjustment):

$$\begin{aligned} \log(\text{titer}) &= \beta_0 + \beta_1 \times \text{PrimeBoost} + \beta_2 \times \text{BoostDose} + \beta_3 \times \text{Interval} + \beta_4 \times (\text{PrimeBoost} * \text{BoostDose}) \\ &+ \beta_5 \times (\text{PrimeBoost} * \text{Interval}) + \beta_6 \times Z + \varepsilon \end{aligned}$$

Where Z is the matrix of covariates age, sex, BMI, and prior receipt of seasonal influenza vaccine as defined in Section 6.4. Subjects missing data for one or more covariates will be excluded from Models 1B and 2B.

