4. INVESTIGATIONAL PLAN

4.1. Overall Study Design and Plan

DMID Protocol 17-0078 follows a Phase II randomized, partially-blinded study design enrolling males and non-pregnant females aged 19 to 50 years of age, inclusive, who are in good health as determined by medical history and physical examination, and meet all eligibility criteria, including erythrocyte sedimentation rate (ESR), hematology, and biochemistry parameter within acceptable range, and negative urine or serum pregnancy test (for females). This clinical trial is designed to assess the safety, reactogenicity and immunogenicity of one or two vaccinations of monovalent inactivated split influenza 2013 and 2017 A/H7N9 virus vaccines (2013 and 2017 A/H7N9 IIVs) manufactured by Sanofi Pasteur (SP), administered intramuscularly at different dosages (3.75 or 15 mcg of HA per dose), given with or without AS03 adjuvant manufactured by GlaxoSmithKline Biologicals (GSK), using different heterologous and homologous prime-boost vaccination schedules.

Subjects will be randomly assigned to 1 of 6 study groups with equal allocation 1:1:1:1:1:1 (see [Table 1](#)). Subjects assigned to Groups 1, 2, and 3 will receive an adjuvanted 2013 A/H7N9 IIV on Day 1 while those in Groups 4, 5, and 6 receive an adjuvanted 2017 A/H7N9 IIV on Day 1. Subjects assigned to Groups 1 and 4 will return approximately 21 days after their first vaccination to receive an adjuvanted 2017 A/H7N9 IIV. Subjects assigned to Groups 2,3,5, and 6 will return approximately after 120 days to receive their second vaccination of 2017 A/H7N9 IIV with or without AS03.

Reactogenicity will be measured by the occurrence of solicited injection site and systemic reactions from the time of each study vaccination through 7 days after each study vaccination. Unsolicited non-serious AEs will be collected from the time of each study vaccination through approximately 21 days after each study vaccination. SAEs and MAAEs, including NOCMCs and PIMMCs, will be collected from the time of the first study vaccination through approximately 12 months after the last study vaccination. Clinical laboratory evaluations for safety will be performed on venous blood collected prior to each study vaccination and approximately 7 days after each study vaccination.

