5. SAMPLE SIZE CONSIDERATIONS

This study is planned to enroll up to 180 subjects. This study is not designed to test a formal null hypothesis. Rather, it is intended to obtain sufficient data to obtain meaningful estimates of the immune response and to uncover any safety issues that occur at a sufficiently high rate that they might be observed in a study of this size. As such, the type I error rate, $\alpha = 0.05$, is not adjusted for multiple comparisons. While this study is not designed to test any specific null hypothesis, the following tables illustrate the precision and power that is available for select estimates and comparisons of interest.

[Table 6](#) indicates the probability of observing one or more safety events, such as solicited injection site or systemic reactogenicity events or an unsolicited non-serious AE of a particular type for a single study group ($N = 30$), or in the trial as a whole ($N=180$).

Binomial confidence intervals (CI) are widest (have the least precision) when the response rate is 50%.

[Table 7](#) is presented to indicate the worst-case scenario for precision of observed exact (Clopper-Pearson) binomial confidence intervals.

[Table 8](#) illustrates the minimum detectable differences in the proportion of subjects responding (e.g. attaining seroconversion or a titer $\geq 1:40$) between any two study groups ($N=30$) using a two-sided Likelihood Ratio Test and $\alpha = 0.05$. It is assumed that up to 10% of subjects ($N=3$) will be excluded from the per protocol analysis. Seroconversion rates of 10% to 50% are considered.

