9.3.1. Solicited Events and Symptoms

Systemic solicited adverse events were collected pre-vaccination, and systemic and local solicited adverse events were collected at-least 20 minutes post-vaccination and then daily for 7 days after each vaccination and graded on a scale of 0 (absent), 1 (mild), 2 (moderate) and 3 (severe). Systemic events include fever, feverishness, fatigue, malaise, myalgia, arthralgia, headache, and nausea. The grading scale for systemic events, including quantitative grading for fever, is included in [Table 11](#). Local events include pruritus, ecchymosis, erythema, induration/swelling, pain, and tenderness. Ecchymosis, erythema, and induration are measured by both functional and measurement grading scales as defined in [Table 10](#).

When calculating the incidence of solicited events, each subject will be counted once at the highest severity following the applicable vaccination, and any repetitions will be ignored. For summaries presented separately for each vaccination, the denominator for percentages will be the number of subjects who received the respective vaccination with non-missing data for the event summarized. For summaries over all vaccinations the denominator will be the number of subjects who received at least one vaccination with non-missing data for the event summarized.

The number and percentage of subjects reporting at least one solicited adverse event of each severity will be summarized for each solicited symptom, any systemic symptom, any local symptom, and any symptoms. For each event the denominator is the number of subjects who received the applicable vaccination with non-missing data for the specific event. The 95% CI calculated using Clopper-Pearson methodology from a binomial distribution (SAS Proc Freq with a binomial option) will be presented ([Table 84](#), [Table 85](#), [Table 86](#)). Logistic regression models will be fit to estimate the effect of prime-boost combination (*PrimeBoost*), Boost dose (*BoostDose*), and interval between vaccinations (*Interval*) on the probability of reporting any local event or reporting any systemic event after either vaccination ([Table 87](#), [Table 88](#)). If statistically significant effects are observed in the model for local events or systemic events, then additional models will be fit for each individual event of that type.

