9.7.1 Sample Size**Table 6: Power (%) to Detect Safety Events**

| Event Frequency | N=30 | N=180 |
|------------------------|-------------|--------------|
| ≥10% Very Common | 95 | >99 |
| ≥1% Common | 26 | 83 |
| ≥0.1% Uncommon | 2 | 16 |
| ≥0.01% Rare | <1 | 1 |

Table 7: Precisions of Binomial Confidence Intervals

| N | 95% CI |
|----------|---------------|
| 30 | 31-69 |
| 180 | 42-58 |

Table 8: Minimum Detectable Difference in Proportion Responders

| N per Group | Proportion Responders in Comparator Group A | 80% Power | |
|-------------|---|-------------------------------|---|
| | | Minimal Detectable Difference | Proportion Responders in Comparator Group B |
| N=27 | 0.10 | 0.32 | 0.42 |
| | 0.20 | 0.35 | 0.55 |
| | 0.30 | 0.38 | 0.68 |
| | 0.40 | 0.37 | 0.77 |
| | 0.50 | 0.34 | 0.84 |

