Tables with similar format:

- Table 57:** Summary of Hemagglutination Inhibition Antibody Against A/Shanghai/2/2013 (A/H7N9) by Study Group and Prior Seasonal Influenza Vaccination at 180 Days Post Second Vaccination, Per Protocol Population
- Table 58:** Summary of Neutralizing Antibody Against A/Shanghai/2/2013 (A/H7N9) by Study Group and Prior Seasonal Influenza Vaccination at 21 Days Post Second Vaccination, Per Protocol Population
- Table 59:** Summary of Neutralizing Antibody Against A/Shanghai/2/2013 (A/H7N9) by Study Group and Prior Seasonal Influenza Vaccination at 180 Days Post Second Vaccination, Per Protocol Population
- Table 60:** Summary of Hemagglutination Inhibition Antibody Against A/Hong Kong/125/2017 (A/H7N9) by Study Group and Prior Seasonal Influenza Vaccination at 21 Days Post Second Vaccination, Per Protocol Population
- Table 61:** Summary of Hemagglutination Inhibition Antibody Against A/Hong Kong/125/2017 (A/H7N9) by Study Group and Prior Seasonal Influenza Vaccination at 180 Days Post Second Vaccination, Per Protocol Population
- Table 62:** Summary of Neutralizing Antibody Against A/Hong Kong/125/2017 (A/H7N9) by Study Group and Prior Seasonal Influenza Vaccination at 21 Days Post Second Vaccination, Per Protocol Population
- Table 63:** Summary of Neutralizing Antibody Against A/Hong Kong/125/2017 (A/H7N9) by Study Group and Prior Seasonal Influenza Vaccination at 180 Days Second Vaccination, Per Protocol Population

Table 64: Logistic Regression Model to Evaluate the Relationship of Administration Schedule with HAI Seroconversion Against A/H7N9 Strains at 21 Days Post Second Study Vaccination, Per Protocol Population

[Implementation Note: Two- and three-way interaction terms will be included in the model at first. If interactions are not significant, fit final model in this table without interaction, and add footnote in table “No interaction terms were significant.”]

| Model Parameter | Parameter Category | A/Shanghai/2/2013 (A/H7N9) | | | | | A/Hong Kong/125/2017 (A/H7N9) | | | | |
|-----------------|------------------------|----------------------------|-------|---------|------------|-----------|-------------------------------|-------|---------|------------|-----------|
| | | Parameter Estimate | SE | p-value | Odds Ratio | 95%CI | Parameter Estimate | SE | p-value | Odds Ratio | 95%CI |
| Intercept | N/A | xxx.x | xxx.x | x.xxx | - | - | xxx.x | xxx.x | x.xxx | - | - |

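### One arm at 0% or 100% makes an interaction in the SAP's logistic models inestimable, and the Table 64 drop rule, if read on Wald p-values, can then delete a real interaction

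*SAP*

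**What the plan says.** SAP 4.1 randomises equally to six study groups. SAP 8.3.2 states: "Logistic regression will be fit for the seroconversion outcome". Model 1A has an intercept, main effects for PrimeBoost, BoostDose and Interval, and the interactions PrimeBoost×BoostDose and PrimeBoost×Interval. Model 1B adds covariates. The section mentions influence diagnostics in PROC LOGISTIC. It names no estimator, no test for the interactions, and no handling of an arm with 0% or 100% responders.

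SAP 9.3.1 fits the same treatment terms to solicited events, "on the probability of reporting any local event or reporting any systemic event after either vaccination". The shells for that model, Tables 87 and 88, are instead titled as post second vaccination.

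The drop rule is only in the implementation note to the Table 64 shell: "If interactions are not significant, fit final model in this table without interaction", with a footnote that no interaction was significant. Tables 65-67 follow the same format. The note also asks for two- and three-way interactions at the start, which the equations in 8.3.2 do not contain. The shell columns are parameter estimate, SE, p-value, odds ratio and 95% CI.

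For planning, SAP 5 takes 27 analysed subjects per arm and a two-sided likelihood-ratio test at 0.05, and adds that "Seroconversion rates of 10% to 50% are considered".

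**The concern.** With as many treatment parameters as arms, the model reproduces each arm's observed rate exactly. An observed rate of 0% or 100% has no finite logit, so any coefficient that uses that arm has no finite maximum-likelihood estimate. Software stops at some large value with a far larger standard error. The Wald p-value then says nothing about the evidence.

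A rule that removes interactions when they are not significant can therefore fail exactly when the interaction is large. The refit forces one common effect of interval, and one of boost dose, on both prime-boost schedules. Whether interval matters differently after a heterologous and a homologous prime is one of the questions these models are meant to address.

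**Working it through.** **1. The plan's own figure.** SAP Table 8 gives detectable pairs at 80% power with 27 per arm: 0.10 v 0.42, 0.20 v 0.55, 0.30 v 0.68, 0.40 v 0.77 and 0.50 v 0.84. I enumerated two binomial(27) arms exactly and rejected when the likelihood-ratio statistic exceeded 3.841. Power is 0.816, 0.794, 0.805, 0.813 and 0.801. The table reproduces with a likelihood-ratio test. The SAP gives no figure for the logistic interaction model.

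**2. Parameters against arms.** The Model 1A design matrix, with the Table 64 reference levels, has rank 6 for six arms. Adding BoostDose×Interval and the three-way term leaves the rank at 6. Neither can be estimated, because no arm gives the 15 mcg boost at 21 days.

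**3. Which arm affects which interaction.** Write G1 to G6 for the arm logits. Inverting the design matrix gives:

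- PrimeBoost×BoostDose = (G2 − G3) − (G5 − G6)
- PrimeBoost×Interval = (G2 − G1) − (G5 − G4)

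Every arm is in at least one line. A single arm 3 or 6 at an extreme makes the first infinite, arm 1 or 4 the second, and arm 2 or 5 both.

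**4. Illustration (assumed counts).** Responders in arms 1-6 are 14, 27, 20, 20, 21 and 15 of 27.

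- Wald test for PrimeBoost×Interval: after 8 iterations the estimate is 8.9 with SE 19, p = 0.64. After 20 iterations it is 20.9 with SE about 7,700, p = 0.998. For PrimeBoost×BoostDose the p-values are 0.71 and 0.998.
- Likelihood-ratio test for PrimeBoost×Interval: without this term, arms 3 and 6 still fit exactly, and arms 1, 2, 4 and 5 must share one interval odds ratio. Responders in arms 1 + 2 and in arms 4 + 5 both total 41. They total 34 in arms 1 + 4 and 48 in arms 2 + 5. The fitted counts are therefore 17, 24, 17 and 24. The statistic is 2 × [14 ln(14/17) + 13 ln(13/10) + 27 ln(27/24) + 20 ln(20/17) + 7 ln(7/10) + 21 ln(21/24) + 6 ln(6/3)] = 2 × 5.98 = 11.96 on 1 df, p = 0.0005.
- The joint likelihood-ratio p for both interactions is 0.001. The Firth penalised likelihood-ratio p for PrimeBoost×Interval is 0.002.

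Read on Wald p-values, both interactions go. Yet the 120-day v 21-day contrast is 27/27 v 14/27 after the heterologous prime and 21/27 v 20/27 after the homologous prime, where the odds ratio is (21/6)/(20/7) = 1.2.

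**5. How often an arm is extreme.** For one given arm of 27, P(27/27) = p^27:

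| True rate | Chance of 100% |
|---|---|
| 0.84 (top of SAP Table 8) | 0.9% |
| 0.90 | 5.8% |
| 0.95 | 25% |

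By symmetry the same values hold for 0% at true rates of 0.16, 0.10 and 0.05. The documents give no expected rate per arm, so these rates are assumptions.

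**6. How often the rule would then err, read on Wald p-values.** These are simulations of 3,000 trials per scenario, restricted to trials with exactly one extreme arm.

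| Assumed scenario | Wald drops, likelihood ratio keeps |
|---|---|
| Arm 2 at 98%, others 50-60% | 100% (all 1,724 trials) |
| Arm 1 at 98% | 87% |
| Arm 5 at 98%, milder interaction | 42% |
| Arm 1 at 98%, with a large real PrimeBoost×BoostDose effect | 2% |

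In the last row the other interaction stays finite and significant, which blocks the refit.

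**The case against.** The strongest reply is that the SAP never says Wald. A reader might infer that maximum likelihood with Wald tests is specified and that a real interaction will be deleted. The text does not go that far. The only test it names for comparing response proportions between groups is the likelihood-ratio test in SAP 5, and under that test the illustration keeps its interaction. This stands: the deletion is conditional on the usual reading of PROC LOGISTIC output and the shell columns. The silence is still a gap in a rule that turns on significance.

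The rule is also narrow. A reader might extend it to the covariate-adjusted Tables 68-71 or the reactogenicity Tables 87-88, but their shells carry no such note. Nor can one lean on every subject receiving an adjuvanted prime to argue that local events will be near 100%: 9.3.1 counts either vaccination, while Tables 87-88 are titled for the second, and Groups 3 and 6 have an unadjuvanted boost.

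A reader might put the risk at 30% or 82%, the chance that at least one of six arms is extreme when all share a true rate of 0.90 or 0.95. With equal rates there is no interaction to delete, so the one-arm figures are the relevant ones.

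Finally, the models are exploratory, the SAP tests no formal hypothesis, and the per-arm rates with exact intervals would show 27/27 openly. A very large SE would also be visible in an unreduced table. That limits the harm, but the reduced table would still carry a wrong footnote.

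**Conclusion.** The point holds in a limited form. It is certain from the design that one arm at 0% or 100% makes at least one interaction estimate infinite under maximum likelihood and its Wald p-value uninformative. It is conditional, on Wald tests being used, that the Table 64 note can delete a real interaction from Tables 64-67. For Tables 68-71 and 87-88 the harm is infinite estimates and uninformative p-values. In Tables 87-88 those p-values also feed the 0.05 trigger for the individual-event models.

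The size depends on rates that the documents do not give. An extreme arm is rare at the top of the planning range (0.9% per arm at 0.84) and a realistic prospect only nearer the limits (5.8% at 0.90, 25% at 0.95). The primary immunogenicity summaries do not change. This is a cheap improvement to an exploratory analysis.

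**What to change.** In SAP 8.3.2, SAP 9.3.1 and the Table 64 note:

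- State that interaction p-values, and the decision to drop interactions, rest on likelihood-ratio tests, with profile-likelihood confidence intervals.
- State that when any arm is at 0% or 100%, the model is fitted by Firth penalised likelihood, with penalised likelihood-ratio p-values and profile penalised-likelihood intervals.
- Remove BoostDose×Interval and the three-way term from the Table 64 note, so that it matches the equations in 8.3.2.

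The cost is a few lines of text and a little extra code. The profile-likelihood options in PROC LOGISTIC supply intervals only, so the p-values need a comparison with the reduced fit. Where Firth is used, the odds ratios shrink slightly.
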